### 13.9 Sponsor-Investigator Responsibility for Reporting Adverse Events

#### 13.9.1 IRB Reporting Requirements

The investigator or designee must report events to the FHCRC IRB in accordance with the policies of the IRB.

### 13.9.2 FDA (IND) Reporting Requirements

The sponsor assumes responsibility for IND safety reporting to the FDA and participating investigators, in accordance with regulations under 21 CFR 312.32.

For determination of IND safety reporting, AE attribution will be assessed according to the suspected adverse reaction definition described in 21 CFR 312.32 as an AE for which there is a reasonable possibility that the drug caused the adverse event where “reasonable possibility” means there is evidence to suggest a causal relationship between the drug and the AE. Suspected adverse reactions that are serious, related, and unexpected will be reported to the FDA as an IND safety report, in accordance with regulations under 21 CFR 312.32.

## 14.0 CRITERIA FOR ENDPOINT EVALUATIONS

### 14.1 Criteria for Evaluation and Endpoints – Lymphoid Malignancies

Responses will be based on the standard criteria for lymphoid malignancies – including the Lugano criteria and the iwCLL response criteria (See Appendix C, D).

#### 14.1.1 Selection of Target Lesions

Up to six of the largest dominant nodes or tumor masses selected according to each of the following:

- Clearly measurable in at least two perpendicular dimensions
- Abnormal lymph nodes are those that are either
  - >15 mm in the greatest transverse diameter (GTD) regardless of the short axis diameter, or
  - >10 mm in the short axis diameter regardless of long axis
- If possible, they should be from disparate regions of the body
- Should include mediastinal and retroperitoneal areas of disease whenever these sites are involved
- Extranodal lesions within the liver or spleen must be at least 1.0 cm in two perpendicular dimensions

#### 14.1.2 PET Scans

Visual assessment currently is considered adequate for determining whether a PET scan is positive. A Deauville score should be reported. In brief, a positive scan is defined as focal or diffuse FDG uptake above background in a location incompatible with normal anatomy or physiology.

#### 14.1.3 Response Criteria

For measurement of response, standard 2014 criteria as described in "Recommendations for Initial Evaluation, Staging, and Response Assessment of Hodgkin and Non-Hodgkin Lymphoma: The Lugano Classification" will be used, and for CLL, the iwCLL response criteria.

## **14.2 Criteria for Endpoint Evaluation – Multiple Myeloma**

Responses will be based on the International Myeloma Working Group criteria for response in multiple myeloma (Appendix E).

## **14.3 Progression-Free Survival**

PFS will be measured as time from first study drug administration to the first occurrence of disease progression or death from any cause. Data for subjects without disease progression or death will be censored at the date of the last tumor assessment and before the initiation of alternative anticancer therapy. The estimates will be formed using the all treated population. Progression-free survival will be calculated using assessments by investigators. Kaplan-Meier methodology will be used to estimate event-free curves and corresponding quartiles (including the median).

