|                             | 
initiating a non-study cancer treatment, withdrawing consent, or becoming lost to follow-up.
 
 
1. Non-Hodgkin Lymphoma: PET-CT and CT (Diagnostic quality) after 2 cycles (8 weeks), then Diagnostic CT of chest, abdomen, and pelvis every 3 cycles (12 weeks) thereafter. Response assessment will be based on the Lugano Criteria 
 
a. Initial response assessment after 2 cycles (8 weeks) with PET-CT and diagnostic CT of chest, abdomen, and pelvis
 
b. Diagnostic CT of the chest, abdomen, and pelvis every 3 cycles thereafter
 
 
 
2. Chronic lymphocytic leukemia: PET-CT and CT (Diagnostic quality) after 2 cycles (8 weeks), then Diagnostic CT of chest, abdomen, and pelvis every 3 cycles (12 weeks) thereafter. A bone marrow aspirate +/- biopsy will only be obtained at screening and to confirm CR. Response assessment based on IWCLL criteria 
 
a. Initial response assessment after 2 cycles (8 weeks) with PET-CT and diagnostic CT of chest, abdomen, and pelvis
 
b. Diagnostic CT every 3 cycles thereafter
 
 
 
3. Multiple myeloma: Assessment of serum protein electrophoresis (SPEP), serum free light chains (sFLC), every 4 weeks. 24-hour urine assessment of Bence-Jones Proteinuria only in subjects who have this as sole marker of disease. Response assessment based on the IMWG. A bone marrow aspirate and biopsy will be obtained at screening and to confirm CR. PET-CT only to be performed amongst subjects with plasmacytoma as the only site of measurable disease, at screening, after 2 cycles, then every 3 cycles thereafter.
 
 |
| Number of trial subjects    | 20  |
| Estimated duration of trial | 105 months (estimated time from first subject enrollment through final subject completion of study intervention, plus 5 years of follow up)   |
| Duration of Participation   | 9 months Subjects will receive treatment with nivolumab until disease progression, unacceptable toxicity, or withdrawal by subject or investigator. Survival, and disease status will be followed for up to 5 years.  |

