### 9.4 Study Response Assessments

Safety assessment will occur through the study and consist of continuous surveillance and recording of adverse events (AEs) and serious adverse events (SAEs).

After the end of treatment, each subject will be followed for 30 days for adverse event monitoring (serious adverse events may be collected for 90 days after the end of treatment). Subjects may have post-treatment follow-up for disease status up to 5 years, or until disease progression, initiating a non-study cancer treatment, withdrawing consent, or becoming lost to follow-up.

4. Non-Hodgkin Lymphoma: PET-CT and CT (Diagnostic quality) after 2 cycles (8 weeks), then Diagnostic CT of chest, abdomen, and pelvis every 3 cycles (12 weeks) thereafter. Response assessment will be based on the Lugano Criteria
  - a. Initial response assessment after 2 cycles (8 weeks) with PET-CT and diagnostic CT
  - b. Diagnostic CT every 3 cycles thereafter
5. Chronic lymphocytic leukemia: PET-CT and CT (Diagnostic quality) after 2 cycles (8 weeks), then Diagnostic CT every 3 cycles (12 weeks) thereafter. A bone marrow aspirate +/- biopsy will be obtained at screening and to confirm CR. Response assessment based on IWCLL criteria
  - a. Initial response assessment after 2 cycles (8 weeks) with PET-CT and diagnostic CT
  - b. Diagnostic CT every 3 cycles (12 weeks) thereafter
6. Multiple myeloma: Assessment of serum protein electrophoresis (SPEP), serum free light chains (sFLC), every 4 weeks. 24-hour urine assessment of Bence-Jones Proteinuria only in subject who have this as sole marker of disease. Response assessment based on the IMWG. A bone marrow aspirate and biopsy will be obtained at screening and to confirm CR. PET-CT only to be performed for subjects with plasmacytoma as the only site of measurable disease at screening, after 2 cycles, then every 3 cycles (12 weeks) thereafter.

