#### 11.1.5.3 End-of-treatment Visit

EOT Visits for all subjects who discontinue from the study should occur at least 7 days, but  $\leq$  30 days, after the last dose of IP and prior to beginning other treatment (+/- 14 days).

The off-study visit will include laboratory studies, medical history, physical exam, remission status, concomitant medications, adverse events, and documentation of any ECI and subsequent management, as in the Study Calendar. All AEs that occur prior to the end-of-treatment visit should be recorded. Subjects with an AE of Grade > 1 will be followed for 30 days. SAEs that occur within 90 days of the end of treatment should also be followed and recorded.

After the end-of-study visit, additional follow-up will be conducted as per routine standard of care for up to 5 years unless other criteria for withdrawal are met. Long-term follow-up may be performed at subjects' local physician's offices. Long-term follow-up will assess survival and disease progression; for clarification, subjects may be contacted by the study team until death, subject withdrawal of consent, lost to follow-up, or study termination, whichever occurs first.

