## 12.0 SUBJECT DISCONTINUATION OF ACTIVE TREATMENT

Subjects may be removed from this study at any time at their discretion. Subjects may also be removed from this protocol if they develop any untoward side effects from the study medications. In addition, there are stopping rules in place for lack of efficacy and excessive toxicity as detailed in the statistical section.

If a subject withdraws consent to participate in the study or aspects of the study, attempts should be made to obtain permission to record survival data up to the protocol-described end of the subject follow-up period. Survival data are important to the integrity of the final study analysis. Documentation in the medical record should state that the subject is withdrawing from the study and what, if any, selected data the subject will permit the investigator to obtain.

An explanation for discontinuing treatment is recorded for each subject discontinuing treatment on the appropriate CRF/eCRF. The Sponsor-Investigator of the study, [name], must be notified immediately if a subject discontinues treatment. All subjects, irrespective of treatment status, will continue to be followed for survival. Treatment in this study must be discontinued for any of the following reasons:

- if the Sponsor decides to stop the study;
- at Investigator's discretion;
- at the subject's request;
- if the subject enrolls in a trial of another investigational agent;
- for disease progression;
- Grade 4 or life-threatening toxicity (See Section 11, Adverse Events and section 9.5 (Table 2)) attributable to study agent;

- pregnancy;

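### PFS (14.3): a subject who starts new therapy without documented progression is censored if alive but counted as an event if death is later recorded, so censoring depends on a future outcome

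*Combined protocol and SAP*

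**What the plan says.** Section 14.3 defines PFS as "time from first study drug administration to the first occurrence of disease progression or death from any cause". Its only censoring rule is one sentence, beginning "Data for subjects without disease progression or death will be censored at the date of the last tumor assessment"; the clause about alternative therapy comes at the end of that same sentence, so that the data of these same subjects "will be censored at the date of the last tumor assessment and before the initiation of alternative anticancer therapy". The planned summaries are Kaplan-Meier curves and their quartiles, including the median.

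The follow-up rules are spread over several sections and do not agree:

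- Section 9.4 allows "follow-up for disease status up to 5 years, or until disease progression, initiating a non-study cancer treatment". The synopsis lists the same end points for disease-status follow-up: "initiating a non-study cancer treatment, withdrawing consent, or becoming lost to follow-up".
- Section 12.0 keeps deaths in view: "All subjects, irrespective of treatment status, will continue to be followed for survival".
- Section 11.1.5.3 sets no stop at new therapy: "Long-term follow-up will assess survival and disease progression; for clarification, subjects may be contacted by the study team until death". Footnote 7 of Appendix A says much the same. Section 9.6 allows up to 5 years of follow-up for both survival and disease status after treatment ends.

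Section 9.0 lists new anticancer therapy separately from progression as a reason for treatment to end, so a switch without progression is foreseen. Section 11.1.1.5.2 collects all new anticancer therapy given after the last dose. No section says how progression or death after new therapy enters PFS.

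**The concern.** Take two subjects with the same course up to the day they start another therapy, neither with documented progression. If one dies a year later and the other is alive at the data cut, 14.3 treats them differently. The first stays at risk until death and has an event then. The second leaves the risk set at the last assessment before the switch. Kaplan-Meier estimation requires that censoring not be decided by what happens afterwards, and here it is.

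If progression is no longer looked for after the switch, the time from switch to death is counted as progression-free. Survival time on the next therapy is then credited to nivolumab. With 20 subjects, a few such cases can shape the tail of the curve.

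**Working it through.** The plan gives no PFS event count, expected median or power, so there is no figure to reproduce. The check has two parts.

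**1. The rules side by side, for a subject who switches without documented progression**

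| Later course | Read with 9.4 and the synopsis (disease follow-up ends at switch) | Read with 9.6, 11.1.5.3 and Appendix A footnote 7 (progression still recorded) |
|---|---|---|
| Alive, no progression recorded | Censored at last assessment before switch | Censored at last assessment before switch |
| Progresses, then dies | Event at death | Event at progression |
| Dies without progression | Event at death | Event at death |

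Censoring depends on the later course in both columns. Unobserved time is counted as progression-free only in the left-hand column.

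**2. Size under the left-hand column (illustration)**

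Inputs:
- Median time to progression 3 months: assumed, not in the documents. Hazard p = ln 2 / 3 = 0.2310 per month.
- Median survival 13.6 or 5.1 months: from Section 3.1, for lymphoma after CD19 CAR T-cell failure, used for scale only. Hazard d = ln 2 / 13.6 = 0.0510 or ln 2 / 5.1 = 0.1359.
- Switch hazard s = 0.05 or 0.10 per month: assumed.
- The three times are independent and exponential.

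Formulas:
- Share switching before progression or death = s / (s + p + d).
- True PFS(t) = exp(−(p + d)t); true median = ln 2 / (p + d).
- PFS as written, if every death is eventually observed: exp(−dt) × [exp(−(s + p)t) + s/(s + p) × (1 − exp(−(s + p)t))]. The second term is the switchers who are still alive.

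First scenario (d = 0.0510, s = 0.05):
- Share switching = 0.05 / 0.3320 = 15%.
- True median = 0.6931 / 0.2820 = 2.46 months. True PFS is exp(−1.692) = 0.18 at 6 months and exp(−3.384) = 0.03 at 12.
- As written at 12 months: 0.5425 × [0.0343 + 0.1779 × 0.9657] = 0.5425 × 0.2061 = 0.112.

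Simulation with deaths counted only to 60 months (400,000 subjects per scenario) gives slightly lower values, because the few switchers alive at 60 months are censored early:

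| Median survival (months) | Switching | Median PFS, as written / true | 6-month PFS, as written / true | 12-month PFS, as written / true |
|---|---|---|---|---|
| 13.6 | 15% | 2.6 / 2.46 | 0.24 / 0.18 | 0.11 / 0.03 |
| 13.6 | 26% | 2.8 / 2.46 | 0.29 / 0.18 | 0.16 / 0.03 |
| 5.1 | 12% | 1.96 / 1.89 | 0.15 / 0.11 | 0.04 / 0.01 |

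In this model, censoring every switcher at the switch returns the true values. Switch hazards of 0.01 to 0.02 (3% to 7% switching, median survival 13.6 months) give 6-month PFS of 0.20 to 0.21 against 0.18.

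**3. A second model, with switching tied to progression**

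Here a share of subjects switch at a random point before they would have progressed. True median PFS is 3.0 months, and survival after progression has a median of 5.1 to 13.6 months. With 20% switching:
- As written: median 3.8 to 4.0 months, 12-month PFS 13% to 18%.
- Censoring every switcher: 3.5 months and 8%.
- True: 3.0 months and 6%.

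The direction is the same. Censoring is closer to the truth than the rule as written but does not recover it.

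**The case against.** Five points can be made for the plan.

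- **The authors probably meant to censor at new therapy.** The closing clause of the censoring sentence suggests so. But the sentence is limited to subjects without an event, and a programmer following it would count the later death. If that was the intent, the rewording only states it.
- **Progression may still be followed after a switch.** Sections 9.6 and 11.1.5.3 and Appendix A footnote 7 set no stop at new therapy. This stands. It means that the upward bias cannot be asserted without a condition.
- **The named summary hardly moves.** Section 14.3 asks for quartiles including the median, and names no 6- or 12-month rate. In the first model the median shifts by about 0.1 to 0.3 months, while its sampling standard deviation with 20 subjects is 0.6 to 1.1 months. This stands for the median. The curve is also to be reported, and its tail moves more: with 26% switching the 12-month gap is 0.16 − 0.03 = 0.13, against a standard deviation of about 0.08.
- **Censoring is not the only defensible rule.** Counting events after a switch is a legitimate treatment-policy approach if progression is still assessed. That is why it belongs as a sensitivity analysis. Censoring is proposed as the main rule because it is the choice 14.3 already makes for event-free switchers.
- **PFS is secondary, in a single arm with no test attached.** Correct. The response-rate test, the sample size and the stopping rules do not depend on it.

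**Conclusion.** The censoring rule in 14.3 depends on a future outcome for subjects who switch without documented progression. That follows from the wording and needs no assumption.

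The upward bias is conditional: it arises if disease follow-up ends at new therapy while deaths continue to be collected. It then lies mainly in the tail: in the base illustration about 0.11 against 0.03 at 12 months, with a median of about 2.6 against 2.45 months. Those sizes rest on an assumed 3-month progression median and assumed switch rates. Subjects who progress before switching already have their event and are unaffected, and the documents do not say how many will switch first.

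A reader might infer that reported PFS will be overstated whatever happens. The documents do not support that, because three places leave room for progression to be recorded after a switch, and the bias then largely disappears. Nor does censoring switchers guarantee the true curve; it does so only if switching is non-informative.

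This should be corrected, but it does not touch the primary analysis.

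**What to change.** 1. Reword 14.3: a subject who starts alternative anticancer therapy before documented progression is censored at the last disease assessment before that therapy, regardless of later progression or death. Other subjects with no event are censored at their last disease assessment.
2. Apply the same rule to duration of response. Section 16.1 analyses it by Kaplan-Meier methods, but Section 14 gives it no censoring rule.
3. Reconcile the synopsis and 9.4 with 9.6, 11.1.5.3 and Appendix A footnote 7 on whether progression is followed after new therapy.
4. Add a sensitivity analysis that counts progression or death after a switch as an event, and report the number of subjects who switch before documented progression.

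Cost: mostly wording. PFS may look slightly shorter, and the main analysis assumes non-informative switching. The start date of new therapy must be recorded. Section 11.1.1.5.2 already collects new therapy, but the calendar in Appendix A schedules that item only at the post-therapy visit, so later switches need a field in long-term follow-up.

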## **14.4 Overall Survival**

Overall survival (OS) will be measured as the time from the first study drug administration to death from any cause.

Data for subjects without death will be censored at the date of the last tumor assessment. Kaplan-Meier methodology will be used to estimate the event-free curves.

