Chimeric antigen T-cells have also been studied in multiple myeloma (MM), though there no FDA approved cellular products as of 2019. There have been several targets used in multiple myeloma, but the most promising thus far has been B cell maturation antigen (BCMA), based on its plasma cell-restricted expression profile. Several groups have studied BCMA CAR T-cells. An early effort by investigators at the National Cancer Institute (NCI) was a phase I clinical trial of BCMA CAR T-cells for relapsed or refractory MM. At the highest dose level,  $9 \times 10^6$  CAR-BCMA T cells/kg, they found an overall response rate of 81%, and median EFS of 31 weeks, with severe cytokine release syndrome in some cases, but mostly reversible. At present, the most developed product is bb2121, a second-generation CAR T-cell product targeting BCMA. Updated results from the Phase 1 trial of bb2121 were presented at the American Society of Clinical Oncology (ASCO) meeting in June 2018, showing remarkable efficacy, with an overall response rate of 95.5% in the highest dose cohort of  $150 \times 10^6$ , and a median progression-free survival for patients at that dose level of 11.8 months.

Unfortunately, despite the initial promise from cellular immunotherapies such as CD19 and BCMA CAR-T cells, the subset of patients who either do not respond, or relapse following therapy, is poor. A recent presentation at ASH examined the outcomes of patients with CD19 expressing lymphomas who underwent CD19 specific CAR T-cell therapy who either did not respond or responded and later progressed. They reported a median OS of 5.1 months for non-responders, and 13.6 months for those who responded and later progressed. These results highlighted the poor outcomes among patients who did not benefit from CD19 CAR-T cells.

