## 9.6 Subject Withdrawal/Discontinuation Criteria

Subjects may withdraw consent at any time for any reason or be dropped from the trial at the discretion of the investigator should any untoward effect occur. In addition, a subject may be withdrawn by the investigator for significant subject noncompliance with protocol requirements, or for administrative and/or other safety reasons. Subjects who require cessation of study therapy but do not withdraw consent may remain in standard follow-up for up to 5 years.

A subject must be discontinued from the trial for any of the following reasons:

- The subject or legal representative (such as a parent or legal guardian) withdraws consent.
- Confirmed radiographic disease progression
- Unacceptable adverse experiences
- Intercurrent illness that prevents further administration of treatment
- Investigator's decision to withdraw the subject
- The subject has a confirmed positive serum pregnancy test
- Noncompliance with trial treatment or procedure requirements
- The subject is lost to follow-up
- Administrative reasons

The End of Treatment and Follow-up visit procedures are listed in Appendix A (Study Calendar) and Section 11.1.5 (Visit Requirements). After the end of treatment, each subject will be followed for 30 days for adverse event and 90 days for serious adverse event monitoring. Subjects may have post-treatment follow-up up to 5 years per routine standard of care for survival and disease status.

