Adverse events will be recorded from the time of a subject signing consent up until 30 days after the last dose of nivolumab, or 90 days after the last dose of nivolumab in the case of serious adverse events.

For subjects with multiple myeloma only.

The Sponsor-Investigator or sub-Investigator may waive screening bone marrow aspirate and biopsy requirements. For subjects with CLL/SLL and MM, repeat bone marrow biopsy only to be done after screening to confirm CR

Pregnancy test is only required in women of childbearing potential. Verbal report of pregnancy will be reported during conduct of the trial.

Tumor assessment imaging (see section 11.1.2.5) will be performed prior to cycle 3 (within 7 days of scheduled treatment dose) and every 3 cycles thereafter. Tumor assessment labs and/or imaging will also be performed as indicated per clinical standard of care (e.g. as appropriate for disease, to evaluate clinical suspicion of disease progression). Screening PET-CT and diagnostic CT done prior to screening up to day -42 may

be used for screening assessment. PET-CT and diagnostic CT will be performed at screening, then after 2 cycles on cycle 2 day 22. Thereafter, tumor assessment will comprise diagnostic CT of chest, abdomen, pelvis every 3 months. For multiple myeloma only, PET-CT should only be done amongst subjects in whom the only measurable disease is by imaging criteria – both at screening and for follow-up.

End of treatment evaluations should be done within 30 days (+/- 14 days) of the last dose of nivolumab or prior to the start of a new anti-cancer drug, whichever is first.

Correlative studies to include peripheral blood for storage for future biomarker analyses. Please see section 15 for details on blood collection and storage.

Long-term follow-up should be done according to the subject's physician standard of care. This may be performed at subjects' local physician's offices. Long-term follow-up will assess survival and disease progression. Subjects may be contacted by the study team until death, subject withdrawal of consent, lost to follow-up, or study termination, whichever occurs first.

If available, will be tested for PD-1 and PD-L1 IHC

The use of growth factors or transfusions to meet hematologic eligibility criteria is allowed

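### OS for subjects without death is censored at the last tumor assessment, which drops known survival time and biases OS downward when many subjects are alive at the analysis

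*Combined protocol and SAP*

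**What the plan says.** Section 14.4 measures OS from first study drug to death from any cause, to be estimated by Kaplan-Meier. Its censoring rule is: "Data for subjects without death will be censored at the date of the last tumor assessment". No other section gives a different rule. Section 16.1 only names Kaplan-Meier and Cox methods for DOR, PFS and OS. Section 14.3 uses the same censoring date for PFS.

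The two kinds of follow-up end at different times.

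- **Disease status.** Section 9.4 allows post-treatment follow-up "for disease status up to 5 years, or until disease progression, initiating a non-study cancer treatment".
- **Survival.** Section 12.0 states: "All subjects, irrespective of treatment status, will continue to be followed for survival". Section 11.1.5.3 adds that "subjects may be contacted by the study team until death, subject withdrawal of consent, lost to follow-up, or study termination". The study calendar in Appendix A has a separate survival-status row under long-term follow-up.

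Some text points to disease assessment after progression. Section 9.6 says: "Subjects may have post-treatment follow-up up to 5 years per routine standard of care for survival and disease status". Appendix A, footnote 7, says: "Long-term follow-up will assess survival and disease progression".

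**The concern.** Last-assessment censoring suits PFS, because progression is seen only when the tumor is assessed. Death is not observed that way. Take two subjects who progress at week 8 and have no later scan. The one who dies at month 10 is an event at month 10. The one alive at month 24 is censored at week 8. Both were followed by the same survival contacts, but the contact counts only if the subject has died.

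Kaplan-Meier assumes that censoring is unrelated to the outcome. Here only survivors leave the risk set early, so later hazards are overstated and the OS estimate is biased down or, at best, unbiased. OS is a named secondary endpoint, and the rule discards survival data that the protocol already collects.

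**Working it through.** The documents give no OS target, landmark rate or event count, so there is no plan figure to reproduce. The check compares Kaplan-Meier under the written rule with Kaplan-Meier censored at last known alive.

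**1. Hand example (invented data).** Twenty subjects: one death at each of months 3 to 12 (10 deaths), and 10 subjects alive at month 24. The estimator is S(t) = ∏(1 − d/n) over death times.

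- Last known alive: 20 at risk at month 3. S(12) = (19/20)(18/19)…(10/11) = 10/20 = 50%; median 12 months.
- Written rule, 5 survivors last scanned at week 8: 15 at risk. S(12) = 5/15 = 33%. The curve first falls to 50% or below at the eighth death (7/15 = 47%), so the median is 10 months.
- Written rule, all 10 survivors last scanned at week 8: 10 at risk. S(12) = 0/10 = 0%. The fifth death gives 5/10, so the median is 7 months. Half the subjects are in fact alive.

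**2. Simulation.** Inputs from the documents:

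- accrual over 36 months (section 5.5);
- scans at 8 weeks, then every 12 weeks (section 9.4);
- as a scale for OS only, section 3.1: "They reported a median OS of 5.1 months for non-responders, and 13.6 months for those who responded and later progressed";
- the trial length in the synopsis: "105 months (estimated time from first subject enrollment through final subject completion of study intervention, plus 5 years of follow up". Taking off the 5 years leaves 105 − 60 = 45 months to the end of study treatment.

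Assumed inputs:

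- uniform entry and 20% responders;
- exponential PFS, with a median of 2 months in non-responders and 6 or 12 months in responders (this gives the ranges below);
- exponential survival after progression, calibrated to the stated total median OS;
- scans stop at the one that detects progression;
- data cuts at 39, 45, 57 and 105 months from first entry.

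Each setting has 200,000 subjects. With a true median OS of 13.6 months:

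| Cut (months) | 24-month OS, written rule | 24-month OS, last known alive | Median, written rule | Median, last known alive |
|---|---|---|---|---|
| 39 | 9-13% | about 25% | 10.8-11.1 | 13.5-13.6 |
| 45 | 12-15% | about 25% | 11.4-11.6 | 13.6 |
| 57 | 17-20% | about 25% | not tabulated | not tabulated |
| 105 | gap about 0.2 points | | | |

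At the 45-month cut, 12-month OS is 47-48% against 55-56%. About 25% of subjects (5 of 20) are alive, and each loses 11-13 months of follow-up on average. If half the subjects keep having scheduled scans after progression, 24-month OS at that cut is 18-20% against about 25%.

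With a true median OS of 5.1 months and a cut at 45 months, 12-month OS is 11.8-15.4% against 12.4-15.9%, and the median does not change.

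**3. Second model.** Time to progression was set at 30% or 50% of mean OS, with the cut counted from last entry and follow-up capped at 60 months. With a true median of 13.6 months:

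- cut at last entry: median 11.3-12.3 months, 24-month OS 8-12% against 21-22%;
- cut 12 months later: median 12.2-13.0 months, 24-month OS 13-16% against 21-22%;
- cut 60 months later: almost no bias.

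The direction and pattern agree with step 2; the size differs somewhat.

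**4. Scale.** With n = 20, the binomial standard error of a 24-month OS of 25% is √(0.25 × 0.75 / 20) = 0.097, about 10 points.

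**The case against.** The direction is hard to dispute, but the size can be argued down.

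- **Timing.** The only horizon in the documents is 105 months, where the gap nearly vanishes. The 39-, 45- and 57-month cuts are assumptions. This stands. Still, 45 months follows from the synopsis as the end of study treatment, and nothing rules out an OS report then.
- **Case mix.** In section 3.1, 13.6 months applies only to patients who responded to CAR T cells and later progressed, and the trial also enrols non-responders. A 50/50 mix of the two medians, cut at 45 months, gives a median of 7.4-7.6 against 7.9-8.1 months and 24-month OS of 6-10% against 13-16%. The median then moves by about half a month, not two. This also stands.
- **Continuing assessments.** Sections 9.6 and 11.1.5.3 and Appendix A allow disease assessment after progression under routine care. This would shrink the bias, roughly by half in the half-scanned run, but such assessments have no schedule.
- **The remedy is incomplete.** Long-term contact has no fixed interval. If deaths are learned promptly but the last contact with survivors is 0-12 months old (an assumption), last-known-alive censoring gives 24-month OS of 20-22% against about 25% at the 45-month cut. About 35-40% of the bias remains. This stands and affects the fix.
- **Noise and weight.** A standard error of about 10 points is comparable to the bias, and no decision rests on OS. But sampling error has no direction, whereas this error does and can be removed.

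**Conclusion.** The concern holds. Section 14.4 as written makes OS censoring depend on the outcome and biases the Kaplan-Meier estimate downward whenever subjects who outlive their last tumor assessment are still alive at the data cut.

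The mechanism is certain; the size is conditional. At a 45-month cut, 24-month OS is understated by about 10-13 points if the true median is 13.6 months, by roughly 6-7 points under an even mix of the two historical medians, and by very little if the median is 5.1 months. After full follow-up the bias is close to nil. These figures rest on the assumed PFS, response rate, survival model and end of scanning. Because the plan sets no OS data cut, the actual size cannot be fixed in advance. This should be corrected, but it does not touch the primary analysis.

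**What to change.** In section 14.4, replace the censoring sentence with one to this effect: subjects without documented death are censored at the date they were last known to be alive, using any study or long-term follow-up contact up to the data cut. Keep last-assessment censoring for PFS in section 14.3 only. State the OS data cut, and plan a survival-status check on all subjects not known to have died close to that date, so that old contacts do not bring part of the bias back. Make the change before any OS analysis.

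The cost is a short text amendment plus one round of survival contacts. Survival status is already part of long-term follow-up in Appendix A, and no study treatment or clinical procedure changes. For OS, the change also removes the question of what counts as a last tumor assessment in myeloma subjects followed by laboratory tests.
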